4.4.2 Exposure, dose intensity and treatment compliance

Study drug exposure will be listed and summarized for acalabrutinib-treated subjects in the SAF. The following summaries will be produced:

- Actual treatment duration
- Summary statistics (n, mean, median, SD, minimum, and maximum) of PID
- Calculated average daily dose

4.4.4 Vital signs

Summary statistics (n, mean, median, SD, minimum, and maximum) for each of the vital signs and the change from baseline at each scheduled post-baseline assessment will be presented by treatment group.

A by-subject listing of all vital sign parameters will be presented; abnormal vital signs will be flagged.

4.4.5 Physical examinations and chest imaging, electrocardiograms and echocardiograms

By-subject listings of all physical examination and weight data will be presented.

If there is a sufficient number of subjects with post-baseline assessments (≥ 10 subjects per treatment group), a shift table of the number and percentage of subjects with normal or abnormal ECG evaluations may be presented from baseline to the most extreme post-baseline evaluation.

By-subject listings of all ECG parameters will be presented along with the heart rhythm and overall evaluation of ECGs at all visits.

By-subject listings of ECHO overall evaluation, abnormalities and LVEF will be presented.

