8.1.5 Physical Examinations and Chest Imaging, Electrocardiogram, and Echocardiogram

The screening physical examination will be symptom-directed and include height, weight and lung auscultation.

Per standard of care, chest imaging can be done by chest x-ray or CT scan with contrast, or any other appropriate means to confirm pneumonia prior to or upon hospitalization (within 7 days of randomization). Post treatment assessment will continue as clinically indicated.

A single 12-lead ECG and will be done during the screening period and at Day 10 or upon discharge from the hospital. ECG should be collected during the treatment period, as clinically

indicated. For all ECGs, details of rhythm, ECG intervals, and an overall evaluation will be recorded.

An echocardiogram should be collected at baseline or during the treatment period, as clinically indicated per SoA. Percentage left ventricular ejection fraction should be recorded.

If the Investigator considers an abnormal ECG or echocardiogram finding at screening or baseline to be clinically significant, that finding should be reported as a concurrent condition.

Any clinically significant abnormal ECG or echocardiogram findings during the treatment period should be recorded in the source document and the AE section of eCRF, according to standard AE collection and reporting processes.

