3.2.4 Physical examinations and chest imaging, electrocardiograms and echocardiograms

Physical examinations and chest imaging, electrocardiograms and echocardiograms will be performed as per SoA and as described in Section 8.1.5 of the CSP.

A 12-lead electrocardiogram (ECG) will be done at screening, Day 10, and as clinically indicated after study entry. All ECGs will be obtained in triplicate. Each ECG will define heart rhythm, P wave duration, PR interval, RR interval, QRS duration, QT interval, QTc and overall evaluation. Baseline is defined, after taking the average of the triplicates, as the averaged triplicate on the date of randomization (Day 1). If no result was obtained on the date of randomization, the latest result prior to the date of randomization is used.

The left ventricular ejection fraction (LVEF) will be reported when echocardiograms (ECHO) are conducted. The LVEF % will also be reported.

Abnormalities recorded at screening or baseline for ECG or ECHO results will be recorded as a concurrent condition. Abnormalities first recorded during the treatment period will be recorded as AEs unless unequivocally related to the disease under study.

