4. ANALYSIS METHODS

4.1 General principles

All statistical analyses will be performed by AZ statistical programming group. Any deviations from the analyses presented in this SAP will be detailed in the clinical study report. All outputs will be produced using SAS® version 9.4 or a later version in accordance with AZ standards.

The below mentioned general principles will be followed throughout the study:

- Demography and baseline characteristics data will be summarised using the FAS.
- All efficacy data will be summarised and analysed using the FAS, unless otherwise specified.
- Safety data will be summarized using the SAF.
- PK data will be summarized using the PKAS.
- CCI [REDACTED]
- Descriptive statistics will be used for all variables, as appropriate.
- Stratification factors age (≥ 65 vs < 65 years) and comorbidities (present vs absent) as recorded at randomization in the IRT system will be used for any summaries or analyses using the FAS that are presented by stratification factor. For summaries or analyses by stratification factor performed using the PPAS, the true stratification results (captured in the eCRF) will be used.
- Continuous variables will be summarised by the number of observations (n), mean, standard deviation (SD), median, minimum and maximum and will be based on non-missing observations. The minimum and maximum will be reported to the same

number of decimal places as the raw data recorded in the database. The mean and median will be reported to one more decimal place than the raw data recorded in the database. The SD will be reported to two more decimal places than the raw data recorded in the database.

- Categorical variables will be summarized by frequency counts and percentages and include the number of subjects with present data and the number of subjects with missing (not present) data. Unless stated otherwise, percentages will be calculated based on the population total for each treatment group. Percentages will be presented to one decimal place.
- For the PK and PD summaries the reported results will be summarized using appropriate significant figures rather than decimal places.
- Baseline is defined as the result obtained on the day of randomization (Day 1). If no result was obtained, the latest result prior to the day of randomization is used. Applies to:
 - Baseline for all laboratory assessments
 - Baseline for vital signs except oxygen saturation (SpO₂)
 - Baseline ECG assessment

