8. APPENDIX

8.1 AESI and ECI definitions

Adverse Event of Special Interest (AESI)

The following preferred terms for the ventricular arrhythmias AESI include:

- Torsade de pointes
- Ventricular arrhythmia
- Ventricular extrasystoles
- Ventricular fibrillation
- Ventricular flutter
- Ventricular tachyarrhythmia
- Ventricular tachycardia

Events of Clinical Interest

The Events of Clinical Interest (ECIs) are from the acalabrutinib program with extended dosing of acalabrutinib in patients with haematologic malignancies.

Category	Subcategory	Definition
Cardiac events		
 • SOC Cardiac disorders
	Atrial fibrillation	
 • PT Atrial fibrillation • PT Atrial flutter
	Ventricular tachyarrhythmias	
 • PT Torsade de pointes • PT Ventricular fibrillation • PT Ventricular flutter • PT Ventricular tachyarrhythmia • PT Ventricular tachycardia
Cytopenias – Anemia		
 • SMQ Haematopoietic erythropenia [narrow + broad]
Cytopenias – Leukopenia		
 • SMQ Haematopoietic leukopenia [narrow + broad]
	Neutropenia	
 • PT Band Neutrophil count decreased • PT Band neutrophil percentage decreased • PT Cyclic neutropenia • PT Febrile Neutropenia • PT Idiopathic neutropenia • PT Neutropenia • PT Neutropenic infection • PT Neutropenic sepsis • PT Neutrophil count decreased • PT Neutrophil percentage decreased
	Other leukopenia	
 • SMQ Haematopoietic leukopenia [narrow + broad] excluding PTs for neutropenia above

Cytopenias - Thrombocytopenia	
 SMQ Haematopoietic thrombocytopenia [narrow + broad]
Hemorrhage	
 SMQ Haemorrhage terms (excl laboratory terms)
Major hemorrhage	
 As per Acerta definition (see below)
Hepatotoxicity	
 SMQ [narrow] Hepatic failure, fibrosis and cirrhosis and other liver damage-related conditions SMQ [narrow] Hepatitis, non-infectious SMQ [narrow] Liver related investigations signs
Hypertension	
 SMQ Hypertension [narrow]
Infections	
 SOC Infections and infestations
Interstitial lung disease/Pneumonitis	
 SMQ [narrow] Interstitial lung disease

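### SAP 4.4.5 commits to no by-arm summary of ECG rhythm or intervals, although protocol 9.6.1 promises tables for all safety assessments

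*SAP*

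**What the plan says.** **Collection.** The Schedule of Activities (protocol 1.1, Tables 1 and 2) has the same ECG row for both arms. Protocol 8.1.5 states: "A single 12-lead ECG and will be done during the screening period and at Day 10 or upon discharge from the hospital". It adds: "For all ECGs, details of rhythm, ECG intervals, and an overall evaluation will be recorded". SAP 3.2.4 is more detailed: "Each ECG will define heart rhythm, P wave duration, PR interval, RR interval, QRS duration, QT interval, QTc and overall evaluation".

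**Baseline.** SAP 3.2.4 states "All ECGs will be obtained in triplicate" and takes the averaged triplicate on the day of randomization, or the latest earlier result, as baseline. SAP 4.1 repeats the day-of-randomization rule and lists "Baseline ECG assessment" under it.

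**Planned output.** The commitment in SAP 4.4.5 is to listings: "By-subject listings of all ECG parameters will be presented along with the heart rhythm and overall evaluation of ECGs at all visits". The only aggregate item applies if at least 10 subjects per group have post-baseline assessments, and even then "a shift table of the number and percentage of subjects with normal or abnormal ECG evaluations may be presented".

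**Governing text.** Protocol 9.6.1 undertakes to tabulate and summarize vital signs and all remaining safety assessments, and leaves the details to the SAP. SAP section 7, on changes from protocol, reads N/A.

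**Adverse event route.** The one AESI is ventricular arrhythmia (protocol 8.6.12); the preferred terms in SAP 8.1 include "Torsade de pointes". Atrial fibrillation and flutter are an ECI subcategory. SAP 4.4.1.1 commits to AESI and ECI summaries by treatment group.

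**The concern.** Safety is a primary objective, the AESI is an arrhythmia, and atrial fibrillation is a named risk (protocol 6.6.7 and Table 5). The scheduled ECG is measured at the same points in both arms and does not depend on a judgement about whether to report an event. If the SAP is followed as written, a shift in an interval or a difference in rhythm between arms need not appear in any table. The reader of the study report would have listings of ECG values, plus arrhythmias as reported by investigators who know the allocation.

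**Working it through.** The plan gives no figure on ECG precision, so the check is mainly a comparison of texts.

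**1. What is collected against what is tabulated.**

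| Item | Collected in both arms | Committed by-arm summary |
|---|---|---|
| Vital signs | yes | yes, values and change from baseline (SAP 4.4.4) |
| Cardiac troponin | yes | yes, values and change from baseline (SAP 4.4.3) |
| Reported AESIs and ECIs | yes | yes (SAP 4.4.1.1) |
| ECG overall evaluation | yes | no; optional shift table only (SAP 4.4.5) |
| ECG rhythm | yes | no; listing only |
| ECG intervals, including QTc | yes | no; listing only |

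An ECG baseline is defined, but no committed table uses it. The DMC outputs in SAP 8.2 contain no ECG item.

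**2. Against the protocol.** Protocol 9.6.1 covers all safety assessments. Listings and an optional table do not meet that undertaking for rhythm and intervals, and SAP section 7 does not record a departure.

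**3. Can the adverse event tables stand in?** Only partly.
- SAP 3.2.4 sends ECG abnormalities first seen during treatment to the AE record, except those unequivocally related to COVID-19. Protocol 8.1.5 sends those that are clinically significant.
- Protocol 8.6.7 restricts AE reporting of deterioration in protocol-mandated procedures to events that are serious or that cause discontinuation of the investigational product. The second condition cannot arise in the BSC arm. The section derives this restriction from the fact that mandated laboratory and vital-sign results are summarised in the study report; no such summary is committed for ECGs. This sits uneasily with protocol 8.1.5 and SAP 3.2.4.
- The study is open-label, so reporting may differ by arm.

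**4. Single or triplicate.** Protocol 8.1.5 has one tracing; SAP 3.2.4 has three, averaged. The two cannot both describe the data. If one tracing was taken, the baseline rule has no triplicate to average.

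**5. Amount of data.** SAP 1.3 reports 62 subjects randomized. Two scheduled ECGs each gives at most 62 × 2 = 124, fewer with deaths and missed visits.

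**6. Would a table be readable at this size?** The documents give no SD for QTc change, so 15 to 30 ms is assumed. The 90% half-width for a difference in mean change is 1.645 × SD × √(2/n), with n evaluable subjects per arm:
- n = 30: 1.645 × 15 × 0.258 = 6.4 ms; with SD 30, 12.7 ms.
- n = 10 (the SAP's threshold for the shift table): 1.645 × 15 × 0.447 = 11.0 ms; with SD 30, 22.1 ms.

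These figures show only that descriptive means by arm would be informative at the planned size. They do not argue for adding an interval estimate.

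**The case against.** The case on the other side is substantial.

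- A reader might infer that the arms are never compared on arrhythmia, or that new atrial fibrillation would be visible only in a listing. The documents do not support that. ECG abnormalities feed the AE record, and ventricular arrhythmias and atrial fibrillation have committed by-arm summaries.
- A reader might also infer that the ECG is the only cardiac measure shared by the arms. It is not: troponin, pulse and blood pressure are scheduled in both and summarized by arm.
- The shift table is a by-group comparison, and with about 30 subjects per arm its threshold of 10 could well be met.
- SAP 4.1 says descriptive statistics apply to all variables as appropriate.
- QT prolongation is not a risk listed in protocol 6.6, is not the AESI, and is not named as an ECI. One preferred term in the AESI list does not make QTc a planned endpoint.
- In Table 5 atrial fibrillation occurred in 4.4% of subjects, with a median first onset of 17.4 months. Dosing here lasts 10 days, so few drug-related cases can be expected.

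Most of this stands, and it limits the point. It does not remove it. The shift table remains optional and omits rhythm and intervals. The clause in 4.1 is general, while 4.4.5 says specifically what ECG output will be produced. The AE route has the gaps shown in the working. Protocol 6.6 itself says the safety profile in COVID-19 may differ from that in the cancer population, and 9.6.1 does not exempt the ECG.

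**Conclusion.** The point holds in a limited form. The SAP commits to no by-arm summary of ECG rhythm or intervals, although they are recorded in both arms against a defined baseline. That falls short of protocol 9.6.1 without being declared. The comparison that remains consists of AE-based AESI and ECI summaries and, if it is produced, a normal/abnormal shift table.

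The consequence is small: no efficacy conclusion, DMC trigger or stopping criterion turns on it. What is missing is a safety comparison that the protocol promised and that existing data can supply. The half-widths rest on an assumed SD and on nearly complete Day 10 or discharge ECGs; the finding itself rests on neither. The single-versus-triplicate contradiction is separate and certain, but the documents do not show which description matches the data collected. Label: cheap improvement.

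**What to change.** In SAP 4.4.5, on the safety set and in the format already used for vital signs in 4.4.4:

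1. Make the normal/abnormal shift table a committed output.
2. Add by-arm descriptive statistics for each ECG interval, including QTc: values, change from baseline to Day 10 or discharge, and change to the worst post-baseline value. State what worst means for each interval, because SAP 4.1 specifies it only for laboratory and vital-sign data.
3. Add the number of subjects per arm with a new rhythm abnormality (atrial fibrillation or flutter, ventricular arrhythmia) on any post-baseline ECG.

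No between-arm test or confidence interval is needed; SAP 4.4 keeps safety descriptive.

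Reconcile protocol 8.1.5 with SAP 3.2.4 on the number of tracings, so that the baseline rule fits the data actually collected. Align 4.4.5 with protocol 9.6.1, or record the departure in SAP section 7.

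The cost is SAP wording and one or two extra tables, with no new ECGs. Locally read ECGs are noisy, which a footnote should say.

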4.4.6 Oxygen treatment, ventilator use and mSOFA

Oxygen treatment and ventilator use data will be used to assess primary and secondary efficacy endpoints of the study.

The number and percentage of subjects requiring oxygen treatment or mechanical ventilation at each timepoint will be presented by treatment group. Oxygen flow rate and method of mechanical ventilation at baseline will also be presented by treatment group. Change from baseline in oxygen flow rate to each post-baseline flow rate and to the maximum post-baseline flow rate will be summarized.

For subjects requiring oxygen treatment, by-subject listings will be presented.

For subjects requiring mechanical ventilation, by-subject listings will be presented on the data collected, as listed in Section [3.2.6](#).

By-subject listings of mSOFA scores and sub-scores may be presented.

[figure not shown]
4.5 Analysis of pharmacokinetics

Plasma concentrations of study drug and/or metabolite will be grouped, tabulated, summarized and plotted, as appropriate. Plasma concentrations will be listed for each subject by nominal time point, as warranted by the data. Additionally, the data will be displayed graphically, as appropriate.

The PK parameters for acalabrutinib and ACP-5862 (such as, AUC and Cmax) may be estimated using a population PK approach, if warranted by the data, and reported separately from the Clinical Study Report (CSR).

Potential correlations of exposure with safety and efficacy outcomes or biomarker measurements may be explored as warranted by the data.

4.6 Analysis of exploratory variables and pharmacodynamics

5. INTERIM ANALYSES

There are no formal interim futility and interim efficacy analyses in this Phase 2 study.

6. DATA MONITORING COMMITTEE

This study will have a DMC. Details of the roles and responsibilities of the DMC and the DMC data review process will be provided in a separate DMC charter. The DMC will be responsible for reviewing the safety data periodically.

The DMC will review the cumulative safety data approximately 28 days after the first 30 subjects (approximately 15 subjects per arm) have been randomized.

In addition, if at any time during the conduct of the study either of the criteria below are met, enrollment of additional subjects will be paused so that the DMC can convene and conduct a full safety review.

- Any death due to acalabrutinib (per Investigator)
- $\geq 20\%$ treatment discontinuation rate due to toxicity attributed to acalabrutinib (per Investigator), when 10 or more acalabrutinib subjects have been treated
- Any Grade 4 hemorrhage due to acalabrutinib (per Investigator)

During the safety review, the DMC will compare the known AE profile associated with acalabrutinib with comprehensive safety data from the current study. The DMC will determine if an unacceptable increase in Grade 3 or higher AEs known to be associated with acalabrutinib has occurred in the study. After their review, the DMC will make a recommendation regarding study continuation, hold, or termination.

At the time of the safety review the DMC will also review all available preliminary efficacy data and will support any health authority interactions or internal discussions based on their review. The study team will remain blinded to the data that the DMC will review until database lock for the primary analysis of the study, which will occur when all randomized subjects have been followed for 38 (± 3) days from randomization.

An updated analysis for those endpoints requiring 90-day assessments will take place after the last randomized subject has had 90 days of follow up from randomization

Details on the outputs that will be provided to the DMC are provided in Section [8.2](#).

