4.4 Internal DMC

This study will have an iDMC. Details of the roles and responsibilities of the iDMC and the safety and efficacy review will be provided in a separate iDMC charter. The iDMC will be responsible for reviewing the safety data periodically.

The iDMC will review the cumulative safety data approximately 28 days after the first 30 subjects (approximately 15 subjects per arm) are randomized.

In addition, if at any time during the conduct of the study either of the criteria below are met, enrollment of additional subjects will be paused such that the iDMC would convene and conduct a full safety review.

- Any death due to acalabrutinib (per Investigator)
- ≥20% treatment discontinuation rate due to toxicity attributed to acalabrutinib (per Investigator), when 10 or more acalabrutinib subjects have been treated
- Any Grade 4 hemorrhage due to acalabrutinib (per Investigator)

During the safety review, the iDMC with compare the known adverse event (AE) profile associated with acalabrutinib with comprehensive safety data from the current study. The iDMC will determine if an unacceptable increase in Grade 3 or higher AEs known to be associated with acalabrutinib occurred in the study. After the review, the iDMC will make a recommendation regarding study continuation, hold, or termination.

At the time of the safety review the iDMC will also review all available efficacy data and will support any health authority interactions or internal discussions based on their review. The study team will remain blinded to the data that the iDMC will review.

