1.3 Number of subjects

The planned total number of subjects in this study is approximately 60. Sixty (60) subjects meeting the eligibility criteria will be randomized in a 1:1 ratio to either Arm 1 (acalabrutinib plus BSC; n=30) or Arm 2 (BSC; n=30).

It is assumed that the proportion of subjects who are alive and free of respiratory failure at Day 14 is 70% under BSC. A targeted difference of 20% between two treatment arms (i.e., 90% for acalabrutinib + BSC) is of clinical interest. With a total sample size of 60, the half-width of the 2-sided 90% confidence interval for the observed treatment difference is 16.4% using unpooled estimate for variance. It has approximately 64% power, with a 2-sided type I error of 0.1, to detect a difference of 20% between the 2 arms.

At the time that the SAP version 3.0 was generated (amendment of version 2.0), the study recruitment was complete with a total of 62 subjects randomized.

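### The 10-subject floor on the discontinuation trigger only delays the prespecified enrolment pause once 2 attributed discontinuations have occurred

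*SAP*

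**What the plan says.** Protocol 4.4 lists criteria that may be met at any time during the study; on any of them, "enrollment of additional subjects will be paused such that the iDMC would convene and conduct a full safety review". One is "≥20% treatment discontinuation rate due to toxicity attributed to acalabrutinib (per Investigator), when 10 or more acalabrutinib subjects have been treated". SAP 6 repeats the rule with the same threshold of 20% and the same minimum of 10, for the "treatment discontinuation rate due to toxicity attributed to acalabrutinib (per Investigator), when 10 or more acalabrutinib subjects have been treated", and with the same consequence: "enrollment of additional subjects will be paused so that the DMC can convene and conduct a full safety review".

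The other two triggers, a death and a Grade 4 hemorrhage that the investigator attributes to acalabrutinib, act on a single event and have no minimum count. There is also one scheduled look: "The DMC will review the cumulative safety data approximately 28 days after the first 30 subjects (approximately 15 subjects per arm) have been randomized".

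Neither document has a version of the discontinuation criterion for fewer than 10 treated subjects. Both leave further detail to a separate committee charter.

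**The concern.** A minimum denominator has a proper purpose in a rate rule. Without one, a single discontinuation among the first 5 treated (1/5 = 20%) would stop enrolment. That reason lapses once a second attributed discontinuation has occurred. With 2 events and fewer than 10 treated, the observed rate is above 20%, and it will still be 20% at the tenth subject if none of the remaining subjects discontinues. The floor can no longer prevent a false alarm; all it does is let more subjects start before the prespecified review.

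What is at stake is the number of further subjects given acalabrutinib between the point at which the outcome of the rule is known and the point at which the rule acts. The protocol says in section 6.6 that the safety profile in COVID-19 is not yet established, and gives early identification of signals as a purpose of monitoring (section 2.2). The first ten treated subjects are where that purpose applies most directly.

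**Working it through.** **Inputs from the documents.** Threshold 20%, inclusive; active from 10 treated acalabrutinib subjects; checked at any time (protocol 4.4, SAP 6). Allocation 1:1, 30 planned per arm (SAP 1.3). The documents state no operating characteristic for this rule, so there is no figure to reproduce.

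**Step 1: what the rule needs.** The smallest count x with x/n ≥ 0.20 is 2 at n = 10, 3 at n = 11-15, 4 at n = 16-20, 5 at n = 21-25 and 6 at n = 26-30. With 2 discontinuations the rate is 100% at n = 2, falling to 22.2% at n = 9 (rule inactive), 20.0% at n = 10 (met) and 18.2% at n = 11 (not met).

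**Step 2: what follows.** If 2 attributed discontinuations stand when fewer than 10 have been treated, the count at the tenth is at least 2, so the rate is at least 2/10. Between 1 and 8 further acalabrutinib subjects can start in the meantime (second event at the ninth or the second treated subject).

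**Step 3: how often, if each outcome were known before the next subject starts.** The true attributed discontinuation rate p is not in the documents; the assumed range is 5% to 40%.

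- P(at least 2 in the first 9) = 1 − (1−p)^9 − 9p(1−p)^8. At p = 0.20: 1 − 0.134 − 0.302 = 0.564.
- P(at least 2 in the first 10) = 1 − (1−p)^10 − 10p(1−p)^9.
- The second event falls on subject t with probability (t−1)p²(1−p)^(t−2). The mean number of further acalabrutinib subjects is the average of 10 − t over t = 2 to 9 with these weights.

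| p | 2 or more in first 9 | 2 or more in first 10 | Mean further subjects, if 2 or more in first 9 |
|---|---|---|---|
| 5% | 7.1% | 8.6% | 3.5 |
| 10% | 22.5% | 26.4% | 3.8 |
| 20% | 56.4% | 62.4% | 4.3 |
| 30% | 80.4% | 85.1% | 4.9 |
| 40% | 93.0% | 95.4% | 5.5 |

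**Step 4: with a reporting lag.** Step 3 is an upper bound, because discontinuations take time to occur and be known. Assume each becomes known 1 to 10 days after the subject starts (uniform), with random (Poisson) arrivals. Accrual is also an assumption: 60 subjects over 56 to 99 days, half of them to acalabrutinib, gives 30/99 = 0.30 to 30/56 = 0.54 per day. Simulation gives:

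| p | Second event known before tenth subject | Acalabrutinib subjects spared, averaged over all trials |
|---|---|---|
| 5% | 4-5% | 0.1-0.15 |
| 10% | 12-16% | 0.3-0.5 |
| 20% | 34-45% | 1.1-1.6 |
| 30% | 56-69% | – |
| 40% | 73-85% | – |

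When the second event does come first, about 3-4 acalabrutinib subjects are spared.

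**The case against.** **The rule does not make enrolment continue.** A reader might infer that enrolment has to go on until the tenth subject, or that 9 discontinuations out of 9 would leave the trial running. The documents do not support that. The rule says when enrolment must pause, not that it must otherwise proceed. The sponsor may stop the study for undue risk (protocol 4.5, Appendix A 9), safety is monitored on an ongoing basis (2.2, Appendix A 5), and serious events are reported within 24 hours (8.6.2). What stands is narrower: nothing prespecified in the two documents acts on this criterion below 10.

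**The pause is not strictly certain.** A reader might also take it as inevitable after 2 events. Attribution can change: protocol Appendix D has potential Hy's Law cases reported as related at first and their causality reassessed later. Enrolment might also stop before 10, or the count might first be checked at 11. These are real conditions, and the conclusion carries them.

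**The charter is not available.** The synopsis says that the committee works to prespecified stopping rules under the charter, which may already provide for earlier action. This cannot be checked.

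**The gap may be rare.** The documents report no dose-limiting toxicities (protocol 2.2). At true rates of 5-10% the gap is uncommon, and the saving averaged over all trials is half a subject or less. This stands; the large percentages apply only to a poorly tolerated drug.

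**Other safeguards cover the serious signals.** The death and hemorrhage triggers act from the first event, but protocol 6.7 also calls for discontinuation for other toxicities, which meet neither trigger. The scheduled review comes after about 15 subjects per arm, past the tenth treated.

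**Conclusion.** The point holds as a limited weakness in the pause rule. It is not a contradiction: protocol and SAP agree, and no stated figure is wrong. With 2 attributed discontinuations before the tenth treated subject, the floor only delays a pause that the rule's own threshold has already determined, on the three conditions given (attribution stands, enrolment reaches 10, count checked at exactly 10). That last condition is itself a weakness: if the check slips by one subject without an event, the rule is no longer met.

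The size depends on a rate, a lag and an accrual speed that the documents do not give. The delay costs about 3-4 acalabrutinib subjects when it occurs and at most 8 (about 16 randomized at 1:1, half of whom receive no acalabrutinib).

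SAP 1.3 records recruitment complete at 62 when version 3.0 was written, so a change in that document alone could spare no one in this trial. The point bears on the protocol rule while enrolment was open and on any reuse of it.

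**What to change.** In protocol 4.4 and SAP 6, and in the charter if it does not already provide for this, let the discontinuation criterion also count as met when 2 or more discontinuations attributed to acalabrutinib toxicity have occurred among fewer than 10 treated subjects. Keep the 20% threshold from 10 onward. A single early event still does not pause enrolment. If outcomes are known as they occur and attribution stands, the chance of a pause by the tenth treated subject is unchanged, because 2 events in the first 10 are needed under either wording; the pause just comes sooner. The change concerns the enrolment pause for committee review and no subject's treatment.

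The cost is one sentence in each document. There are two drawbacks: the committee would meet with fewer subjects to review, and enrolment could pause for an event that is later re-attributed.
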